8.1.2 Telephone contact (Week -2)

The investigator (or designee) should contact the subject by telephone 2 weeks following Visit 1 to assess continued eligibility and will remind the subject of the importance of accurate seizure diary completion. During the telephone contact, the following assessments will be performed:

- Inclusion/exclusion criteria
- AE reporting
- Concomitant medications and AEDs
- Withdrawal criteria

8.2 Treatment Period

The Treatment Period continues until 1 of the following occurs (whichever occurs first):

- Completion of ≥ 6 weeks of the Treatment Period and occurrence of ≥ 2 PGTC seizures
- Completion of 24 weeks of the Treatment Period without occurrence of 2 PGTC seizures
- The 125th event occurs in the study

8.2.1 Visit 2 (Day 0) Randomization

All assessments at Visit 2 (Day 0) should be conducted prior to the first dose of study drug. During Visit 2 (Day 0), the following assessments will be performed:

- Inclusion/exclusion criteria
- Randomization
- Body weight
- Physical examination (complete)
- Neurological examination (complete)
- ECG 12-lead assessment (see Section 10.3.1)
- Vital signs (pulse rate, systolic BP, and diastolic BP, including orthostatic assessments)
- C-SSRS assessment (for subjects ≥ 6 years of age)
- Blood and urine samples for clinical laboratory assessments (includes hematology, chemistry, endocrinology, urinalysis, and a urine pregnancy test [for women of childbearing potential])
- Subject diary return/review
- Dispense subject diary
- Dispense study drug
- Achenbach CBCL
- BRIEF-P/BRIEF
- EQ-5D-3L
- QOLIE-31-P/PedsQL
- Healthcare resource use
- Work/school days lost due to epilepsy
- Days with help from a caregiver due to epilepsy
- Socio-professional data
- Tanner Stage (will be performed only for subjects who are pubescent at Visit 2 or who enter puberty during the course of the study)
- AE reporting
- Concomitant medications and AEDs
- Withdrawal criteria
- Contact IRT

The subject will take the first dose of study drug in the clinic.

8.2.2 Titration Period

8.2.2.1 Week 1 to Week 6

Both clinic visits and telephone contacts will be conducted during the Titration Period, beginning with a telephone contact at the end of Week 1 and continuing through clinic Visit 5 at the end of Week 6.

At each clinic visit and telephone contact, the investigator, in conjunction with the subject and/or parent(s)/legal representative(s), will decide how to proceed with study drug dosing based on tolerability (including vital signs, body weight, 12-lead ECG, and AE reporting, as applicable to the type of visit contact). If the withdrawal of study drug is required during the Titration Period, the subject will enter the blinded Taper Period (Table 7-5).

8.2.2.1.1 Telephone contact (Week 1, Week 3, Week 5, and unscheduled)

The following assessments will be performed during telephone contacts (both scheduled [Week 1, Week 3, and Week 5] and unscheduled) during the Titration Period:

- AE reporting
- Concomitant medications and AEDs
- Withdrawal criteria

8.2.2.1.2 Visit 3 (end of Week 2)

During Visit 3 (end of Week 2), the following assessments will be performed:

- Body weight
- Physical examination (brief)
- Neurological examination (brief)
- ECG 12-lead assessment (see Section 10.3.1)
- Vital signs (pulse rate, systolic BP, and diastolic BP, including orthostatic assessments)
- C-SSRS assessment (for subjects ≥ 6 years of age)
- Blood and urine samples for clinical laboratory assessments (includes hematology, chemistry, urinalysis, and a urine pregnancy test [for women of childbearing potential])
- Subject diary return/review
- Dispense subject diary
- Dispense study drug
- Study drug review/return
- Healthcare resource use
- Work/school days lost due to epilepsy
- Days with help from a caregiver due to epilepsy
- Socio-professional data

-
- AE reporting
 - Concomitant medications and AEDs
 - Withdrawal criteria
 - Contact IRT

8.2.2.1.3 Visit 4 (end of Week 4)

During Visit 4 (end of Week 4), the following assessments will be performed:

- Body weight
- Physical examination (brief)
- Neurological examination (brief)
- ECG 12-lead assessment (see Section 10.3.1)
- Vital signs (pulse rate, systolic BP, and diastolic BP, including orthostatic assessments)
- C-SSRS assessment (for subjects ≥ 6 years of age)
- Urine pregnancy test (for women of childbearing potential)
- Subject diary return/review
- Dispense subject diary
- Dispense study drug
- Study drug review/return
- Healthcare resource use
- Work/school days lost due to epilepsy
- Days with help from a caregiver due to epilepsy
- Socio-professional data
- AE reporting
- Concomitant medications and AEDs
- Withdrawal criteria
- Contact IRT

8.2.3 Maintenance Period

8.2.3.1 Visit 5 (end of Week 6)

During Visit 5 (end of Week 6), the following assessments will be performed:

- Body weight
- Physical examination (brief)
- Neurological examination (brief)

-
- ECG 12-lead assessment (see Section 10.3.1)
 - Vital signs (pulse rate, systolic BP, and diastolic BP, including orthostatic assessments)
 - C-SSRS assessment (for subjects ≥ 6 years of age)
 - Blood and urine samples for clinical laboratory assessments (includes hematology, chemistry, urinalysis, a urine pregnancy test [for women of childbearing potential], and LCM plasma concentration)
 - Subject diary return/review
 - Dispense subject diary
 - Dispense study drug
 - Study drug review/return
 - Healthcare resource use
 - Work/school days lost due to epilepsy
 - Days with help from a caregiver due to epilepsy
 - Socio-professional data
 - AE reporting
 - Concomitant medications and AEDs
 - Withdrawal criteria
 - Contact IRT

8.2.3.2 Visit 6 (end of Week 8)

During Visit 6 (end of Week 8), the following assessments will be performed:

- Body weight
- Physical examination (brief)
- Neurological examination (brief)
- Vital signs (pulse rate, systolic BP, and diastolic BP, including orthostatic assessments)
- C-SSRS assessment (for subjects ≥ 6 years of age)
- Urine pregnancy test (for women of childbearing potential)
- Subject diary return/review
- Dispense subject diary
- Dispense study drug
- Study drug review/return
- Healthcare resource use
- Work/school days lost due to epilepsy

-
- Days with help from a caregiver due to epilepsy
 - Socio-professional data
 - AE reporting
 - Concomitant medications and AEDs
 - Withdrawal criteria
 - Contact IRT

8.2.3.3 Visit 7 (end of Week 12)

During Visit 7 (end of Week 12), the following assessments will be performed:

- Body weight
- Physical examination (brief)
- Neurological examination (brief)
- ECG 12-lead assessment (see Section 10.3.1)
- Vital signs (pulse rate, systolic BP, and diastolic BP, including orthostatic assessments)
- C-SSRS assessment (for subjects ≥ 6 years of age)
- Blood and urine samples for clinical laboratory assessments (includes hematology, chemistry, urinalysis, and a urine pregnancy test [for women of childbearing potential])
- Subject diary return/review
- Dispense subject diary
- Dispense study drug
- Study drug review/return
- Healthcare resource use
- Work/school days lost due to epilepsy
- Days with help from a caregiver due to epilepsy
- Socio-professional data
- AE reporting
- Concomitant medications and AEDs
- Withdrawal criteria
- Contact IRT

8.2.3.4 Visit 8 (end of Week 16)

During Visit 8 (end of Week 16), the following assessments will be performed:

- Body weight
- Physical examination (brief)

-
- Neurological examination (brief)
 - Vital signs (pulse rate, systolic BP, and diastolic BP, including orthostatic assessments)
 - C-SSRS assessment (for subjects ≥ 6 years of age)
 - Urine pregnancy test (for women of childbearing potential)
 - Subject diary return/review
 - Dispense subject diary
 - Dispense study drug
 - Study drug review/return
 - Healthcare resource use
 - Work/school days lost due to epilepsy
 - Days with help from a caregiver due to epilepsy
 - Socio-professional data
 - AE reporting
 - Concomitant medications and AEDs
 - Withdrawal criteria
 - Contact IRT

8.2.3.5 Visit 9 (end of Week 20)

During Visit 9 (end of Week 20), the following assessments will be performed:

- Body weight
- Physical examination (brief)
- Neurological examination (brief)
- ECG 12-lead assessment (see Section 10.3.1)
- Vital signs (pulse rate, systolic BP, and diastolic BP, including orthostatic assessments)
- C-SSRS assessment (for subjects ≥ 6 years of age)
- Blood and urine samples for clinical laboratory assessments (includes hematology, chemistry, urinalysis, and a urine pregnancy test [for women of childbearing potential])
- Subject diary return/review
- Dispense subject diary
- Dispense study drug
- Study drug review/return
- Healthcare resource use
- Work/school days lost due to epilepsy

-
- Days with help from a caregiver due to epilepsy
 - Socio-professional data
 - AE reporting
 - Concomitant medications and AEDs
 - Withdrawal criteria
 - Contact IRT

8.2.3.6 Visit 10/ET Visit (end of Week 24)

Once the subject has experienced 2 PGTC seizures, the site should contact the Medical Monitor to confirm whether the subject has met the exit criteria. If the exit criteria are met, sites will be advised to have subjects return for their ET Visit within 1 week of the subject's second seizure. Once the 125th event occurs subjects will return to the site at the next scheduled visit and the ET/Visit 10 will be performed (see Section 6.3).

During the Visit 10/ET Visit (end of Week 24), the following assessments will be performed:

- Body weight
- Height
- Physical examination (complete)
- Neurological examination (complete)
- ECG 12-lead assessment (see Section 10.3.4)
- Vital signs (pulse rate, systolic BP, and diastolic BP, including orthostatic assessments)
- C-SSRS assessment (for subjects ≥ 6 years of age)
- Blood and urine samples for clinical laboratory assessments (includes hematology, chemistry, endocrinology, urinalysis, a serum pregnancy test [for women of childbearing potential], and LCM plasma concentration)
- Subject diary return/review
- Dispense subject diary
- Dispense study drug
- Study drug review/return
- Achenbach CBCL (same version used at Visit 2)
- BRIEF/ BRIEF-P (same version used at Visit 2)
- EQ-5D-3L (for subjects ≥ 12 years of age)
- QOLIE-31-P/PedsQL (same version used at Visit 2)
- Healthcare resource use
- Work/school days lost due to epilepsy

-
- Days with help from a caregiver due to epilepsy
 - Tanner Stage (will be performed only for subjects who are pubescent at Visit 2 or who enter puberty during the course of the study)
 - Socio-professional data
 - AE reporting
 - Concomitant medications and AEDs
 - Withdrawal criteria
 - Contact IRT

8.3 End of Study Period

8.3.1 Transition Period

8.3.1.1 Transition Clinic Visit/telephone contact

A Transition telephone contact is required. The following assessments will be performed during the Transition telephone contact:

- AE reporting
- Concomitant medications and AEDs
- Withdrawal criteria

A Transition Clinic Visit is optional, at the discretion of the investigator. Subjects requiring a clinic visit will have the same assessments conducted as an Unscheduled Visit (see Section 8.4).

8.3.1.2 Final Clinic Visit

After completing ≥ 6 weeks and experiencing the second PGTC seizure during the Treatment Period or after completing the 24-week Treatment Period or the 125th event occurs in the study (whichever comes first), eligible subjects may, at the ET Visit or Visit 10 (Week 24) respectively, choose to continue in EP0012. Subjects completing Visit 10 (Week 24) or the ET Visit must complete a 4-week blinded transition followed by a Final Clinic Visit. The Final Clinic Visit is the same as Visit 1 of EP0012. Subjects choosing to enter EP0012 must sign and date the EP0012 extension IRB/IEC-approved informed consent prior to receiving EP0012 study drug.

During the Final Clinic Visit, the following assessments will be performed:

- Body weight
- Height
- Physical examination (complete)
- Neurological examination (complete)
- ECG 12-lead assessment (see Section 10.3.1)
- Vital signs (pulse rate, systolic BP, and diastolic BP, including orthostatic assessments)
- C-SSRS assessment (for subjects ≥ 6 years of age)

-
- Blood and urine samples for clinical laboratory assessments (includes hematology, chemistry, endocrinology, urinalysis, and a urine pregnancy test [for women of childbearing potential])
 - Subject diary return/review
 - Healthcare resource use
 - Work/school days lost due to epilepsy
 - Days with help from a caregiver due to epilepsy
 - Socio-professional data
 - AE reporting
 - Concomitant medications and AEDs
 - Study drug return/review
 - Withdrawal criteria
 - Contact IRT

8.3.2 Taper and Safety Follow-up Period

8.3.2.1 End of Taper Visit

Subjects completing Visit 10 (Week 24) or the ET Visit who choose not to continue in EP0012 must complete an up to 4-week blinded taper followed by the End of Taper Visit. At the End of Taper Visit, the following assessments will be performed:

- Body weight
- Physical examination (complete)
- Neurological examination (complete)
- ECG 12-lead assessment (see Section 10.3.1)
- Vital signs (pulse rate, systolic BP, and diastolic BP, including orthostatic assessments)
- C-SSRS assessment (for subjects ≥ 6 years of age)
- Blood and urine samples for clinical laboratory assessments (includes hematology, chemistry, urinalysis, and a urine pregnancy test [for women of childbearing potential])
- Subject diary return/review
- Study drug review/return
- Healthcare resource use
- Work/school days lost due to epilepsy
- Days with help from a caregiver due to epilepsy
- Socio-professional data
- AE reporting

- Concomitant medications and AEDs
- Withdrawal criteria
- Contact IRT

8.3.2.2 Safety Follow-up Visit

Following the End of Taper Visit, the subject will return 2 weeks (± 2 days) after the last dose of study drug for a Safety Follow-up Visit. In case the 125th event occurs in the study, the subjects discontinuing treatment will complete a 30-day Safety Follow-up Period in the EP0012 study. The 30-day Safety Follow up Period will be done as part of EP0012, except if the subject refuses to sign the EP0012 informed consent form. If the subject signs the informed consent form for a short Safety Follow-up as part of EP0012, the 30-day Safety Follow-up will be performed as part of EP0012; otherwise, the Safety Follow-up will be performed in SP0982.

During the Safety Follow-up Visit, the following assessments will be performed:

- Body weight
- Physical examination (complete)
- Neurological examination (complete)
- ECG 12-lead assessment (see Section 10.3.1) (required only for subjects with an abnormal reading at the previous clinic visit)
- Vital signs (pulse rate, systolic BP, and diastolic BP, including orthostatic assessments)
- C-SSRS assessment (for subjects ≥ 6 years of age)
- Blood and urine samples for clinical laboratory assessments (includes hematology, chemistry, endocrinology [required only for subjects with an abnormal value at the previous clinic visit], urinalysis, and a urine pregnancy test [for women of childbearing potential]).
- Healthcare resource use
- Work/school days lost due to epilepsy
- Days with help from a caregiver due to epilepsy
- Socio-professional data
- AE reporting
- Concomitant medications and AEDs

8.3.2.3 Safety Follow-up telephone contact

Thirty days (-1/+3 days) after the last dose of study drug, the subject will receive a Safety Follow-up telephone contact. In case the 125th event occurs in the study, the subjects discontinuing treatment will complete a 30-day Safety Follow-up Period in the EP0012 study. The 30-day Safety Follow up Period will be done as part of EP0012, except if the subject refuses to sign the EP0012 informed consent form. If the subject signs the informed consent form for a short Safety Follow-up as part of EP0012, the 30-day Safety Follow-up will be performed as part of EP0012; otherwise, the Safety Follow-up will be performed in SP0982.

During the Safety Follow-up telephone contact, the following assessments will be performed:

- AE reporting
- Concomitant medications and AEDs

8.4 Unscheduled Visit

Unscheduled Visits may be performed at any time after Visit 1, as clinic visits or telephone contacts, at the discretion of the investigator. During an Unscheduled Visit, the following assessments are required:

- AE reporting
- Concomitant medications and AEDs
- Withdrawal criteria
- Contact IRT

If an Unscheduled Visit is due to an AE, then the C-SSRS (for subjects ≥ 6 years of age) is required.

In addition to the required assessments listed above, depending on the type of visit (clinic or telephone), further assessments can be completed as needed and may include ECG, vital signs, laboratory tests, dispense study drug, diary review, etc.

9 ASSESSMENT OF EFFICACY

9.1 Primary efficacy variable

The primary efficacy variable is the time to the second PGTC seizure during the 24-week Treatment Period.

9.2 Secondary efficacy variables

The key secondary efficacy variable is:

- Seizure freedom for PGTC seizures during the 24-week Treatment Period, estimated using Kaplan-Meier analysis

The other secondary efficacy variables are:

- The percent change in PGTC seizure frequency per 28 days during the first 6 weeks of the Treatment Period (Titration Phase) relative to the Combined Baseline (combined 12-week Historical and 4-week Prospective Baseline)
- The percent change in PGTC seizure frequency per 28 days during the Treatment Period relative to the Combined Baseline
- Time to the first PGTC seizure during the Treatment Period

9.3 Other efficacy variables

Other efficacy variables are:

- Change in days with absence seizures per 28 days during the Treatment Period relative to the Prospective Baseline

-
- Percent change in days with absence seizures per 28 days during the first 6 weeks of the Treatment Period (Titration Period) relative to the Prospective Baseline
 - Percent change in days with absence seizures per 28 days during the Treatment Period relative to the Prospective Baseline
 - Percentage of subjects with at least a 50% reduction in absence seizure days compared to Prospective Baseline
 - Change in days with myoclonic seizures per 28 days during the Treatment Period relative to the Prospective Baseline
 - Percent change in days with myoclonic seizures per 28 days during the first 6 weeks of the Treatment Period (Titration Period) relative to the Prospective Baseline
 - Percent change in days with myoclonic seizures per 28 days during the Treatment Period relative to the Prospective Baseline
 - Percentage of subjects with at least a 50% reduction in myoclonic seizure days compared to Prospective Baseline
 - Seizure-free status (yes, no) for PGTC seizures for the first 12 weeks of the Treatment Period
 - Seizure-free status (yes, no) for PGTC seizures for the 24-week Treatment Period
 - Percentage of subjects with at least a 50% reduction in PGTC seizure frequency during the first 12 weeks of the Treatment Period compared to Combined Baseline
 - Percentage of subjects with at least a 50% reduction in PGTC seizure frequency during the Treatment Period compared to Combined Baseline
 - Seizure-free status (yes, no) for all generalized seizure types for the first 12 weeks of the Treatment Period
 - Seizure-free status (yes, no) for all generalized seizure types for the 24-week Treatment Period
 - Change from Baseline in QOLIE-31-P subscale (Seizure Worry, Daily Activities/Social Functioning, Energy/Fatigue, Emotional Well-being, Mental Activity/Cognitive Functioning, Overall Quality of Life and Medication Effects) and total scores in subjects ≥ 18 years of age or change from Baseline in the PedsQL subscale (Physical Functioning, Emotional Functioning, Social Functioning, and School Functioning) and total scores in subjects < 18 years of age
 - Change from Baseline to end of treatment or ET in the EQ-5D-3L VAS score and change in utility as converted from the 5 dimensions (for subjects ≥ 12 years of age)
 - Healthcare resource use: medical procedures, hospitalizations, and healthcare provider visits
 - Number of working or school days lost by subject due to epilepsy
 - Number of days with help from a caregiver due to epilepsy

9.3.1 Seizure variables

Subjects will keep a diary to record daily seizure activity from Visit 1 until the end of study participation. Efficacy and safety variables will be assessed using the seizure count information recorded on the subject diaries. Subjects should be reminded that diaries must include daily entries even if no seizures have occurred. The subject should be reminded to bring the diary to each clinic visit.

9.3.1.1 PGTC seizures

The following information will be recorded on a daily basis as applicable:

- Seizure type
- Number of PGTC seizures

If more than 1 PGTC seizure occurs on a single day, each seizure should be counted separately, provided there is a complete recovery of consciousness between seizures.

9.3.1.2 Absence and myoclonic seizures

In the subject diary, the following information will be recorded on a daily basis:

- Seizure type
- Number of seizures to be recorded although for the purpose of data analysis, only the number of days with seizure will be analyzed.

Investigators should advise subjects and/or caregivers about the importance of reporting absence and myoclonic seizures.

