4.1.3 Other efficacy variables

Other efficacy variables are:

- The percent change in PGTC seizure frequency per 28 days during the first 6 weeks of the Treatment Period (Titration Phase) relative to the Combined Baseline (combined 12-week Historical and 4-week Prospective Baseline)

-
- The percent change in PGTC seizure frequency per 28 days during the first 12 weeks of the Treatment Period relative to the Combined Baseline
 - The percent change in PGTC seizure frequency per 28 days during the Treatment Period relative to the Combined Baseline
 - Change in days with absence seizures per 28 days during the Treatment Period relative to the Prospective Baseline
 - Percent change in days with absence seizures per 28 days during the first 6 weeks of the Treatment Period (Titration Phase) relative to the Prospective Baseline
 - Percent change in days with absence seizures per 28 days during the Treatment Period relative to the Prospective Baseline
 - Percentage of subjects with at least a 50% reduction in absence seizure days compared to Prospective Baseline
 - Change in days with myoclonic seizures per 28 days during the Treatment Period relative to the Prospective Baseline
 - Percent change in days with myoclonic seizures per 28 days during the first 6 weeks of the Treatment Period (Titration Phase) relative to the Prospective Baseline
 - Percent change in days with myoclonic seizures per 28 days during the Treatment Period relative to the Prospective Baseline
 - Percentage of subjects with at least a 50% reduction in myoclonic seizure days compared to Prospective Baseline
 - Seizure-free status (yes, no) for PGTC seizures for the first 12 weeks of the Treatment Period
 - Seizure-free status (yes, no) for PGTC seizures for the 24-week Treatment Period
 - Percentage of subjects with at least a 50% reduction in PGTC seizure frequency during the Titration Period compared to Combined Baseline
 - Percentage of subjects with at least a 50% reduction in PGTC seizure frequency during the first 12 weeks of the Treatment Period compared to Combined Baseline
 - Percentage of subjects with at least a 50% reduction in PGTC seizure frequency during the Treatment Period compared to Combined Baseline
 - Seizure-free status (yes, no) for all generalized seizure types for the first 12 weeks of the Treatment Period
 - Seizure-free status (yes, no) for all generalized seizure types for the 24-week Treatment Period

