4.2 Safety variables

The safety variable is:

- AEs as reported spontaneously by the subject and/or caregiver or observed by the investigator.

Other safety variables are:

- Subject withdrawal due to AE
- Incidence of new seizure types during the Treatment Period
- Subjects with an increase of up to 25%, >25% to 50%, >50% to 75%, and >75% in the days with absence seizures per 28 days during the Treatment Period relative to the Prospective Baseline
- Subjects with an increase of up to 25%, >25% to 50%, >50% to 75%, and >75% in the days with myoclonic seizures per 28 days during the Treatment Period relative to the Prospective Baseline
- Changes in hematology, chemistry, endocrinology, and urinalysis parameters
- Changes in 12-lead ECGs
- Changes in vital sign measurements (ie, blood pressure [BP] and pulse rate) (including body weight and height) and physical and neurological examination findings
- Behavioral assessment (Achenbach CBCL/1½-5 or CBCL/6-18) for pediatric subjects only
- Cognitive function assessment (BRIEF-P or BRIEF) for pediatric subjects only

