5.1.1 Study duration per subject

The maximum duration of study drug administration is 28 weeks. The study will last a maximum of 36 weeks per subject, consisting of the following study periods:

- 4-week Prospective Baseline Period
- 6-week (minimum) to 24-week (maximum) Treatment Period (including a 6-week titration)
- 4-week End of Study Period consisting of either:
 - 4-week blinded transition (required for subjects participating in EP0012)
 - Up to 4-week blinded taper followed by a 30-day Safety Follow-up Period (required for subjects not participating in EP0012)
 - Subjects can enter EP0012 after the completion of Visit 10 (Week 24) or ET Visit and a 4-week blinded transition. Subjects who choose not to continue in EP0012 must complete an up to 4-week blinded taper followed by a 30-day Safety Follow-up Period (see Section 7.2.4).

Titration Period

In case the 125th event occurs in the study while subjects are still in their 6-week Titration Period, these subjects will not have to proceed to Week 6 prior to initiating the Transition/Taper Period; these subjects will also be invited for their ET Visit at the next scheduled visit.

Maintenance Period

In case the 125th event occurs in the study while subjects are in their Maintenance Period, these subjects will also be invited for their ET Visit at the next scheduled visit and enter the Transition/Taper Period.

Transition Period

In case the subject is in the Transition/Taper Period, these subjects will proceed to their scheduled completion visit.

Screening Period

In case the 125th event occurs while a subject is in screening, the subject may proceed to the scheduled Baseline Visit if they are eligible or are a Baseline failure; these subjects will be able to enter EP0012 and will not proceed to randomization in SP0982 but will enter EP0012. For the subjects entering EP0012, their next visit will be Visit 1.

The end of the study is defined as the date of the last visit of the last subject in the study.

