13.7 Planned interim analysis and data monitoring

Some AEDs with sodium channel blocking properties can exacerbate some generalized seizure types, such as absence and myoclonic seizures. To enhance safety monitoring, 3 interim analyses are planned when 25%, 50%, and 75% of subjects experience an event (31, 62, and 93 events, respectively) or 24 weeks after 50, 100, and 150 subjects have been randomized, respectively, whichever comes first. An event is defined as the occurrence of the second PGTC seizure during the Treatment Period.

Three interim analyses for safety will be performed by the IDMC with a single futility assessment planned at the second interim analysis. The IDMC will oversee the safety of the study by reviewing safety data periodically. Details will be provided in an IDMC charter. Both safety and futility will be assessed in a manner that ensures that blinding is not compromised for individuals involved with operational aspects of the study, or individuals involved with the planning and conduct of the final statistical analyses. Analysis of the primary endpoint (time to second PGTC seizure) will only be examined at the planned futility assessment; an unblinded, descriptive review of safety, PGTC seizure frequency, and changes in days with absence and/or myoclonic seizures will be provided for all IDMC meetings.

Additional details, including the methods used for assessing futility, will be provided in the interim SAP. Neither futility or the IDMC safety assessments are expected to have any impact on the Type 1 error as there will be no stopping rule for success in place; however, the significance level will be set using a Haybittle-Peto boundary at $\alpha=0.0001$ so as not to require any adjustment to the overall alpha level for the final analysis.

The IDMC will consist of 3 voting members, none of whom will be involved with the conduct of the study, either by management or participation. In addition, there will be an independent reporting team, consisting of an independent statistician and statistical programmers, who will be completely independent from the blinded reporting team. The blinded reporting team will be responsible for all operational aspects of the study, including routine monitoring and cleaning of the data, programming, and quality control (QC) of all analyses defined in the interim SAP on blinded data.

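### Absence and myoclonic worsening is measured from the diary in seizure days alone, so the upper safety bands close from 16, 19 and 23 baseline days although daily counts are recorded

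*Protocol*

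**What the plan says.** Section 9.3.1.2 sets the scale for absence and myoclonic seizures: "Number of seizures to be recorded although for the purpose of data analysis, only the number of days with seizure will be analyzed". The diary-based frequency variables for these two types follow it:

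- Section 4.2 grades worsening in four bands: "Subjects with an increase of up to 25%, >25% to 50%, >50% to 75%, and >75% in the days with absence seizures per 28 days", and applies the same bands "in the days with myoclonic seizures per 28 days during the Treatment Period relative to the Prospective Baseline".
- Section 4.1.3 lists "Change in days with absence seizures per 28 days during the Treatment Period relative to the Prospective Baseline", with a myoclonic counterpart and percent-change and responder versions, all in days.
- Section 13.7 gives the IDMC an unblinded review in which "changes in days with absence and/or myoclonic seizures will be provided for all IDMC meetings".

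The reference is the "4-week Prospective Baseline Period" (Section 5.1.1). Section 13.7 gives the reason for watching these types: "Some AEDs with sodium channel blocking properties can exacerbate some generalized seizure types, such as absence and myoclonic seizures". No count-based variable for absence or myoclonic seizures is listed.

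**The concern.** Aggravation of these seizure types is the harm that the protocol itself names as its reason for enhanced safety monitoring. Section 2 adds that about 10% of subjects in the uncontrolled pilot study had more absence seizures, and that drug effect could not be separated from natural course. This trial supplies the missing control arm.

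A days scale has a ceiling. Someone with seizures on many baseline days has little room to move, and a rise in seizures within a day leaves the measure unchanged. Neither the inclusion nor the exclusion criteria limit absence or myoclonic frequency, and Section 5.4.4 counts absence and juvenile myoclonic epilepsies among the common IGE syndromes. Near-daily seizures at baseline are therefore allowed. For such subjects the graded bands would understate a worsening that the diary has recorded.

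The word *only* in Section 9.3.1.2 fixes this in the protocol; it is not a detail left for the SAP.

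**Working it through.** The protocol gives no figure of its own on this point. Its 125-event sizing is not an input.

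**Inputs**
- Scale: days with seizure per 28 days, maximum 28 (Sections 4.2 and 9.3.1.2).
- Band limits: 25%, 50% and 75% (Section 4.2).
- b = baseline seizure days per 28, from the 4-week Prospective Baseline.

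**Step 1: largest possible increase.** If every treatment day has a seizure, the increase is (28 − b)/b.

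| b | (28 − b)/b | Highest band open |
|---|---|---|
| 14 | 14/14 = 100% | >75% |
| 15 | 13/15 = 86.7% | >75% |
| 16 | 12/16 = 75.0% | >50% to 75% |
| 18 | 10/18 = 55.6% | >50% to 75% |
| 19 | 9/19 = 47.4% | >25% to 50% |
| 22 | 6/22 = 27.3% | >25% to 50% |
| 23 | 5/23 = 21.7% | up to 25% |
| 25 | 3/25 = 12.0% | up to 25% |
| 27 | 1/27 = 3.7% | up to 25% |
| 28 | 0/28 = 0% | none |

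**Step 2: where each band closes.** An increase above x needs b < 28/(1 + x).
- 75%: 28/1.75 = 16, so closed from 16 days.
- 50%: 28/1.50 = 18.7, so closed from 19 days.
- 25%: 28/1.25 = 22.4, so closed from 23 days.

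These are outer bounds, because they assume a seizure on every treatment day.

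**Step 3: illustration below the ceiling (assumption, not in the protocol).** If daily counts are Poisson with mean m, expected days are 28(1 − e^−m). Doubling m then gives:
- m = 0.25: 6.2 to 11.0 days, +78%.
- m = 1: 17.7 to 24.2 days, +37%.
- m = 2: 24.2 to 27.5 days, +14%.
- m = 3: 26.6 to 27.9 days, +5%.

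Under this assumption a true doubling (+100% in counts) falls in the top band at 0.25 per day, in the >25% to 50% band at 1 per day, and in the mildest band at 2 or more per day. If seizures cluster within days, these figures change; the cut-points in Step 2 do not.

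**The case against.** A reader might infer that anyone with seizures on most baseline days cannot register a worsening, however many more seizures follow. The arithmetic does not support that. Most of 28 days means 15 or more, and at 15 days even the top band is open (86.7%). The bands close one after another, and only 28 of 28 days rules out any increase. What never registers, at any baseline, is a further seizure on a day that already counts.

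A reader might also infer that worsening is captured through days alone. It is not:
- Section 10.1.1.3 makes worsening of an existing seizure type an adverse event of special interest.
- Section 10.1.1.1 makes a clinically significant rise in frequency or intensity an adverse event, with no day cap, and Section 10.1.2 asks the investigator to review diary cards.
- Section 4.2 puts adverse events first and the day bands among the other safety variables. Section 13.4 summarises treatment-emergent events by arm.
- Section 6.4 lists worsening seizure frequency among the possible reasons for withdrawal.
- Section 13.7 lets the IDMC ask for further tables, and the counts exist.
- The pilot-study absence signal was itself reported through adverse events (Section 2).

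All of this stands. These routes rest on investigator judgement, however, and on a request being made. They do not give a pre-specified, diary-based comparison between arms, which is what the Section 4.2 bands are for.

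Two further objections also stand. Days are a consistent choice across the protocol and less noisy than counts, so they are a reasonable main scale. And entry requires PGTC seizures, not absence or myoclonic ones, so the subgroup near the ceiling may be small.

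**Conclusion.** The point holds as a limitation of the analysis scale. The days-only rule makes the Section 4.2 bands above 75%, 50% and 25% unreachable from 16, 19 and 23 baseline days, and the seizure-day changes shown to the IDMC have the same ceiling. Those cut-points need no assumption beyond the 28-day cap. The dilution below the ceiling rests on the assumed Poisson process and is illustrative.

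How much this would hide cannot be computed, because the protocol does not give the share of subjects near the ceiling. It also gives no ground for saying that subjects with near-daily seizures are the ones most exposed to aggravation, so that reading should not be drawn.

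The primary analysis, error rate, power and sample size are untouched, and no rule of clinical management is in question. This is an inexpensive improvement that would let the trial use data it already records to quantify the harm it names.

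**What to change.** In Section 9.3.1.2, replace the restriction to days with a statement to this effect: *Days with seizure are the main scale. For the safety variables in Section 4.2 and the IDMC tables, the recorded number of absence seizures and of myoclonic seizures per 28 days will also be summarised descriptively by arm, as change and ratio to the Prospective Baseline. These summaries are supportive and will also be shown for subjects with 16 or more baseline seizure days per 28, for whom the band above 75% cannot be reached.* The ratio applies to subjects with at least one such seizure at baseline. Add matching lines in Sections 4.2 and 13.7.

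The cost is a few extra descriptive tables from diary data already recorded. The downside is that counts of absence and myoclonic seizures are noisier than days, which is why they should not replace days.
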